10.2 Key Secondary Efficacy Variable(s) and Analysis

Not applicable.

10.3 Other Secondary Efficacy Variable(s) and Analysis

All secondary efficacy variables are listed as following:

- Cumulative Attack Severity. This score is the sum of the maximum symptom severity recorded for each angioedema attack in a treatment period.
- Cumulative Daily Severity. This score is the sum of the severity scores recorded for every day of reported symptoms in a treatment period.
- Number of angioedema attacks requiring acute treatment during each treatment period.
- Change from pre- to post-dose in C1 INH functional activity, C1 INH antigen, and C4 levels.

The endpoints based on attack severity are further defined with the following example:

Study Day	Symptoms Present	Maximum ^a Symptom Severity	Symptom Severity Score	Attack Number	Maximum ^b Attack Severity	Daily Severity
1	Yes	Moderate	2	1	-	2
2	Yes	Moderate	2		2	2
3	No					
4	Yes	Mild	1	2	-	1
5	Yes	Severe	3		-	3
6	Yes	Moderate	2		3	2
7	No					
8	Yes	Moderate	2	3	-	2
9	Yes	Severe	3		-	3
10	Yes	Moderate	2		-	2
11	Yes	Moderate	2		3	2

^a Maximum Severity across all anatomic locations on the corresponding study day.

^b Maximum Severity across all anatomic locations and days with symptoms for the corresponding attack.

In this hypothetical example, a patient recorded 9 days of symptoms in an 11-day study period. Because individual attacks require at least one symptom-free calendar day between episodes, this diary fragment identifies three angioedema attacks. The maximum severity of each attack is determined on the last day of symptoms and is derived as Mild, Moderate, or Severe. Coding these categories as Mild=1, Moderate=2, and Severe=3 and summing over the three unique attacks, yields a Cumulative Attack Severity of 8. Finally, summing the reported severity scores of each attack multiplied by the duration of each attack a Cumulative Daily Severity of 37. With respect to these defined endpoints, this hypothetical eleven-day symptom diary would be quantitatively described by:

Endpoint	Value
Number of Angioedema Attacks	3
Cumulative Attack Severity	8
Cumulative Daily Severity	37

For the secondary efficacy variables of Cumulative Attack Severity, Cumulative Daily Severity, and number of angioedema attacks requiring acute treatment, the analysis method will be the

same as the primary variable using the normalized numbers (per month) calculated by following steps --

Any subject who completes a randomized treatment period should provide data with which to derive efficacy scores. Thus, for each individual treatment period, let,

X_i = Number of **days** of participation in that treatment period for Subject i ,

Y_i = **RAW** Efficacy Score expressing the cumulative period score for Subject i ,

Y^*_i = **NORMALIZED** Efficacy Score for Subject i , (expressed as score per **Day**),

Y^\dagger_i = **SCALED** Normalized Efficacy Score for Subject i , (expressed as score per **Month**),

Then,

$Y^*_i = Y_i \div X_i$ (the normalized score, expressed as the score per **Day**),

$Y^\dagger_i = Y^*_i \times 30.4$ (the scaled normalized score, expressed as the score per **Month**).

In this study, after obtaining the duration of participation (X_i) in each patient-specific treatment period, the following array can be constructed for the following four efficacy endpoints:

Efficacy Variables	Raw Score	Normalized Score	Scaled Score
Number of Angioedema Attack	Y_{1i}	Y_{1^*i}	$Y_{1^\dagger_i}$
Cumulative Attack Severity	Y_{2i}	Y_{2^*i}	$Y_{2^\dagger_i}$
Cumulative Daily Attack Severity	Y_{3i}	Y_{3^*i}	$Y_{3^\dagger_i}$
Number of Angioedema Attacks Requiring Acute Treatment	Y_{4i}	Y_{4^*i}	$Y_{4^\dagger_i}$

The Scaled normalized score will be used for all tabulations, summaries, and analyses involving efficacy data.

For available data in observation period, the summary statistics will be provided for efficacy endpoints along with the treatment periods. Change from observation period in normalized number of angioedema attacks during treatment will be summarized as well.

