1.0 INTRODUCTION

Hereditary angioedema (HAE) is an autosomal dominant disease resulting from mutations of the C1 inhibitor (C1 INH) gene and deficient plasma C1 INH protein. Nearly all affected individuals experience symptoms of the disease; however, the symptoms vary in both their frequency and severity (Gompels et al., 2005; Zuraw, 2003). The diagnosis of a C1 INH deficiency is suggested by a history that includes recurrent attacks of angioedema, characterized by non-itching swelling of the skin or mucosa. Serum C4, C1 INH antigen, and functional C1 INH levels can be measured to assist with the diagnosis of HAE. A low level of C4 in combination with a low level of either C1 INH antigen (Type I HAE) or functional C1 INH (Type II HAE) are confirmatory for the diagnosis of HAE (Frank et al., 1976). In rare instances, C4 levels may be normal in HAE patients between attacks, but are almost always decreased during episodes of HAE swelling (Frank et al., 1976). In this circumstance, a low serum C4 level during an episode of idiopathic swelling can be used to confirm the diagnosis of HAE (Frank et al., 1976; Waytes et al., 1996).

Attacks of HAE are usually self-limiting, but can be quite painful, disfiguring, disabling, and sometimes fatal. Edema can involve the skin and visceral organs, but most frequently manifests in the extremities or bowel; the swelling generally lasts 2 to 5 days (Nzeako et al., 2001; Zuraw, 2008). Abdominal attacks have been reported to occur in >93% of patients and account for nearly 50% of all angioedema attacks (Zuraw, 2008). Not infrequently, an abdominal HAE attack can imitate a surgical emergency. Life-threatening laryngeal edema may also occur and this accounts for the majority of the 30% to 40% mortality rate reported for this disease (Agostoni and Cicardi, 1992; Bork et al., 2000).

Intravenous administration of C1 INH, the plasma protein that is deficient in patients with HAE, has been used in Europe for more than 30 years for the treatment of acute attacks of HAE (Wall and Frank, 1990; Gadek et al., 1980). C1 INH concentrates are prepared from pooled human plasma. The efficacy of purified C1 INH concentrates in the treatment of acute angioedema in HAE has previously been described (Agostoni et al., 1980; Bergamaschini et al., 1983; Logan and Greaves, 1984; Späth et al., 1984).

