6.10.1 Recording of Angioedema Attacks

During the observation period and both treatment periods, parents/caregivers will use the eDiary each day to record any symptoms or occurrences of an angioedema attack experienced by the subject. The Investigator will complete a separate angioedema attack eCRF for each attack based upon their review of the data in the eDiary and include:

- Characterization of whether swelling or pain is (indicate all that apply):
 - Mucosal (pharyngeal, laryngeal, gastrointestinal, genitourinary)
 - Non-mucosal (truncal, external, facial)
- Location (site) of the swelling or pain (indicate all that apply):
 - Upper airway (includes laryngeal or pharyngeal)
NOTE: pharyngeal or oral swelling that results in airway compromise will be classified as a laryngeal attack
 - Gastrointestinal/abdominal (including symptoms of pain, nausea, vomiting, swelling, and/or change in bowel habits)
 - Genitourinary (including scrotum or vulva)
 - Facial
 - Extremity or peripheral (e.g., buttocks, external head/neck, trunk)

- Severity (intensity) of the sign/symptom at each location listed:
 - None
 - Mild: the angioedema attack sign/symptom(s) is noticeable but is easily tolerated by the subject and does not interfere with routine activities.
 - Moderate: angioedema attack sign/symptom(s) interferes with the subject's ability to attend school or participate in family life and social/recreational activities.
 - Severe: the angioedema attack sign/symptom(s) significantly limits the subject's ability to attend school or participate in family life and social/recreational activities.
- Angioedema attack trigger(s)
- Answer the question, “Was treatment administered for the attack?” If yes, record treatment administered.

In addition to recording the above information, study personnel will report any angioedema attack that occurs after the first dose of study drug as an AE (see Section 9.0).

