7.3 Efficacy Analysis

All efficacy endpoints will be determined for each subject in each treatment period:

- Number of angioedema attacks, normalized to a 12-week treatment period
- Cumulative Attack Severity. This score is the sum of the maximum symptom severity recorded for each angioedema attack in a treatment period.
- Cumulative Daily Severity. This score is the sum of the severity scores recorded for every day of reported symptoms in a treatment period.
- Time (measured in days from the first dose of study drug in a treatment period) to the first angioedema attack reported in that treatment period.
- Change from pre- to post-dose in C1 INH functional activity, C1 INH antigen, and C4 levels.
- Number of angioedema attacks requiring acute treatment during each treatment period.

The endpoints based on attack severity are further defined with the following example:

Study Day	Symptoms Present	Maximum ^a Symptom Severity	Symptom Severity Score	Attack Number	Maximum ^b Attack Severity	Daily Severity
1	Yes	Moderate	2	1	-	2
2	Yes	Moderate	2		2	2
3	No					
4	Yes	Mild	1	2	-	1
5	Yes	Severe	3		-	3
6	Yes	Moderate	2		3	2
7	No					
8	Yes	Moderate	2	3	-	2
9	Yes	Severe	3		-	3
10	Yes	Moderate	2		-	2
11	Yes	Moderate	2		3	2

a: Maximum Severity across all anatomic locations on the corresponding study day.

b: Maximum Severity across all anatomic locations and days with symptoms for the corresponding attack.

In this hypothetical example, a patient recorded 9 days of symptoms in an 11-day study period. Because individual attacks require at least one symptom-free calendar day between episodes, this diary fragment identifies three angioedema attacks. The maximum severity of each attack is determined on the last day of symptoms and is derived as Mild, Moderate, or Severe. Coding these categories as Mild=1, Moderate=2, and Severe=3 and summing over the three unique attacks, yields a Cumulative Attack Severity of 8. Finally, summing the

reported severity scores over the 9 days with symptoms yields a Cumulative Daily Severity of 19. With respect to these defined endpoints, this hypothetical eleven-day symptom diary would be quantitatively described by:

Endpoint	Value
Number of Attacks	3
Cumulative Attack Severity	8
Cumulative Daily Severity	19

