17. CHANGES TO ANALYSES SPECIFIED IN PROTOCOL

Analysis populations to analyses specified in the protocol are modified in using Shire standard definition and wording for SAP. Details are presented in Section 4.1, Section 4.2, Section 4.3, Section 4.4, and Section 4.5.

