18.2 Derived Efficacy Variables

Not applicable.

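### SAP 10.3 gives two incompatible rules for Cumulative Daily Severity, and its worked value of 37 follows from neither

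*SAP*

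**What the plan says.** The definition bullet in SAP 10.3 reads: "This score is the sum of the severity scores recorded for every day of reported symptoms in a treatment period". Protocol 7.3 defines the endpoint in the same way, and both documents illustrate it with the same eleven-day diary.

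From there they part. The protocol concludes that summing the "reported severity scores over the 9 days with symptoms yields a Cumulative Daily Severity of 19". The SAP replaces that sentence with "summing the reported severity scores of each attack multiplied by the duration of each attack a Cumulative Daily Severity of 37", and it repeats 37 in the small endpoint table that follows. The SAP introduces the example as a further definition of the severity endpoints, so the narrative has the force of a rule.

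Later in SAP 10.3 the raw score is divided by days of participation and multiplied by 30.4. The section then says: "The Scaled normalized score will be used for all tabulations, summaries, and analyses involving efficacy data".

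On changes from the protocol, SAP Section 17 says: "Analysis populations to analyses specified in the protocol are modified in using Shire standard definition and wording for SAP". SAP 12.7 declares one further change, the formal PK/PD analysis, which is moved outside the study report. Neither section mentions Cumulative Daily Severity. The section headed "18.2 Derived Efficacy Variables" is marked as not applicable.

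**The concern.** A worked example exists so that a programmer can test code against it. Here, code that follows the definition bullet returns 19 and fails the test, and code that follows the narrative fails it too under either natural reading. The number therefore cannot show which rule was meant.

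The two readings of the narrative distort the score in different ways. Summed scores times duration counts duration twice, so it over-weights long attacks. Maximum times duration counts duration once but replaces each daily score with the attack's worst day, so it inflates attacks whose severity varies. Neither is a constant multiple of the daily sum, so the choice can change the sign of a subject's difference between doses.

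The endpoint is analysed by the same methods as the primary variable, with 12 subjects planned. It enters the scaled efficacy outputs (Tables 3.1 to 3.3 with their a and b versions, Table 3.5, Figure 3.3 and Listing 6.1). Table 3.2, Figure 3.3 and Listing 6.1 are marked for the EU PIP output, so the ambiguity can also reach the report on the first 6 subjects.

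**Working it through.** **Inputs** (example table, the same in SAP 10.3 and Protocol 7.3; Mild = 1, Moderate = 2, Severe = 3):

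- Attack 1, days 1–2: scores 2, 2 (sum 4, maximum 2, duration 2)
- Attack 2, days 4–6: scores 1, 3, 2 (sum 6, maximum 3, duration 3)
- Attack 3, days 8–11: scores 2, 3, 2, 2 (sum 9, maximum 3, duration 4)

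**The plan's other example figures.** There are 3 attacks, and Cumulative Attack Severity is 2 + 3 + 3 = 8. Both reproduce, so the diary is being read correctly.

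**Cumulative Daily Severity under each rule:**

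| Rule | Calculation | Result | Relative to 19 |
|---|---|---|---|
| Daily sum (SAP bullet, Protocol 7.3) | 4 + 6 + 9 | 19 | – |
| Maximum × duration | 2×2 + 3×3 + 3×4 = 4 + 9 + 12 | 25 | +32% |
| Printed in the SAP | none given | 37 | +95% |
| Summed scores × duration | 4×2 + 6×3 + 9×4 = 8 + 18 + 36 | 62 | +226% |

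The protocol's 19 reproduces; the SAP's 37 does not. Counting duration as days minus 1 or days plus 1 does not help: summed scores give 43 or 81, and maxima give 17 or 33.

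Two constructions do reach 37, but neither is stated anywhere: (sum minus maximum) × duration = 2×2 + 3×3 + 6×4 = 37, and maximum × duration with attack 3 counted twice = 4 + 9 + 12 + 12 = 37. Because more than one works, the intended rule cannot be recovered from the number.

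**Can the order of two periods change?** Using only attacks like those in the diary:

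| Comparison | Daily sum | Maximum × duration | Summed scores × duration |
|---|---|---|---|
| Attack 3 alone vs attacks 1 and 2 | 9 vs 10 | 12 vs 13 | 36 vs 26 |
| Attack 2 alone vs two attacks like attack 1 | 6 vs 8 | 9 vs 8 | 18 vs 16 |

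The first comparison reverses under summed scores × duration only; the second reverses under both readings. On the SAP's monthly scale over 84 days (score ÷ 84 × 30.4), the first is 3.26 vs 3.62 by daily sum and 13.03 vs 9.41 by summed scores × duration.

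**Weight given to longer attacks.** Protocol 1.0 states that "the swelling generally lasts 2 to 5 days". For a constant moderate attack of 2, 3, 4 or 5 days, the daily sum and maximum × duration both give 4, 6, 8, 10. Summed scores × duration gives 8, 18, 32, 50. Under that reading a typical attack is multiplied by 2 to 5, depending on its length.

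**The case against.** The best reply is that the intent is not really in doubt. SAP Section 1 says the SAP elaborates the analyses in the protocol. The SAP bullet, its Daily Severity column and Protocol 7.3 all point to the daily sum, and Section 17 declares no change to the endpoint. The faulty sentence even lacks its verb, which suggests an unfinished edit. A careful programmer would probably query it and follow the bullet. This makes harm less likely, but the sentence was actively rewritten from the protocol's wording and the value changed in two places, so it cannot be dismissed as a stray digit.

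A second reply is that if severity meant the attack's mean daily score, severity times duration would equal the daily sum. That is true, but the SAP does not say mean, and the result would be 19, not 37.

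Third, the sentence does not mention the attack maximum, so the 25 rests on a substitution, and the reversals use hand-picked periods. This is fair as a limit: the reversals show what is possible, not what is likely. The second comparison does, however, also reverse under summed scores times duration.

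Fourth, the endpoint ranks low. SAP 10.2 names no key secondary endpoint, and the paired t-test needs 12 or more completers. That bears on severity. The mixed model carries no such condition, so the endpoint may still be tested.

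Finally, one eCRF per attack is not evidence that daily scores are lost: the eDiary is completed every day, and its handling is assigned to a separate Data Management Plan. That stands, and the data check below is a confirmation, not a claimed gap.

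**Conclusion.** The concern holds. SAP 10.3 contradicts its own definition and Protocol 7.3, and the printed 37 is wrong under the definition (19) and under both natural readings of the sentence beside it (25 and 62). The daily sum is the likelier intent, but the SAP does not say so consistently, and any intended change is undeclared.

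On the example the discrepancy ranges from +32% to +226%, with the printed value at +95%. Those percentages belong to a hypothetical diary, and the size of the effect in the trial cannot be estimated from the documents. What the arithmetic establishes is that the rules are not proportional and can reverse a within-subject comparison. The attack count, Cumulative Attack Severity and the number of attacks needing acute treatment are unaffected. This should be fixed before the endpoint is programmed.

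**What to change.** In SAP 10.3, restore the protocol's sentence for this endpoint, change 37 to 19 in the text and in the endpoint table, and program the plain sum of the daily maximum severity scores.

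If a severity-by-duration measure was intended, write it as one unambiguous formula, make the bullet and the example agree with it, and declare the departure from the protocol in Section 17.

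In either case, confirm that day-level severity from the eDiary reaches the analysis data. Protocol 6.10.1 says: "The Investigator will complete a separate angioedema attack eCRF for each attack based upon their review of the data in the eDiary". If only one severity per attack were transferred, the daily sum could not be calculated.

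The cost is one sentence, two printed values and a data check, plus a Section 17 entry if a new rule is adopted.

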10.4 Exploratory Efficacy Variable(s) and Analyses

Not applicable.

11. SAFETY ANALYSES

The safety analyses will be performed by treatment using the Safety Set. Safety endpoints include AEs, clinical laboratory variables, vital signs, and C1 INH antibody variables. For each safety variable, the last value collected prior to the first dose of the investigational product will be used as baseline for all analyses of that safety variable.

Summary statistics and changes from baseline to post-baseline for laboratory testing and vital signs by dose group will be presented. Adverse events by dose group, by dose group (dose normalized to body weight [U/kg]), and by time of onset (e.g., during administration of study drug or within 24 hours after the end of injection of study drug) will be summarized. Results of C1 INH antibody testing will be reported for individual subjects and summarized as appropriate.

Final on Treatment Assessment (LAoT) will be defined as the last observation recorded within the period in which the treatment is administered.

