- a: Study drug administration and scheduled procedures will occur twice weekly (every 3 or 4 days) during the 12-week treatment period (Treatment Period 1, Visits 1a-24a).
- b: Specified study procedures and blood samples should be performed/collected prior to study drug administration, on the same day.
- c: Randomization will occur on Dosing Day 1 (Visit 1a) prior to the first dose of study drug in Treatment Period 1.
- d: Medical history will be updated prior to randomization at Visit 1a. Physical examinations will be targeted based on reporting of adverse events and performed in accordance with standards at the site.
- e: Vital signs will be measured using standard methods at each study site. On dosing days, vital signs should be obtained prior (within 60 minutes) to the injection of study drug and between 10 to 30 minutes after completion of the injection of study drug. Additional vital signs measurements may be performed if clinically indicated.
- f: Body temperature should be measured prior to randomization at Visit 1a.
- g: HIV (single assay antibody/Western Blot) and hepatitis (Hepatitis B Surface Antigen, Hepatitis C Antibody).
- h: Pregnancy testing (urine) will be performed on females who have reached menarche.
- i: Study drug will be administered by/under supervision of qualified personnel to all subjects at the investigational site for Dosing Visits 1a, 12a, and 24a.
- j: For those subjects who are administered study drug at a location other than the study site, study personnel will contact the parent/caregiver by telephone on Weeks 3 and 9 (after Dosing Visits 6a and 18a, respectively) to discuss and document study compliance, tolerability of CINRYZE dose, and adverse events. All telephone contacts will be documented in the source notes at the clinical site.
- k: **In addition, subjects should complete the EQ-5D-Y on each day that they experience signs or symptoms of an angioedema attack.**

See Schedule 4 for details regarding clinical assessments at early discontinuation (if applicable), 1-week post-treatment, and 1-month post-treatment follow-up visits.

In the event a subject prematurely discontinues from treatment and/or the study, Early Discontinuation Visit procedures will be performed as soon as possible.

NOTE: Investigators will report all SAEs to Shire VIROPHARMA Drug Safety through 30 days after the last dose of study drug and SAEs considered related to study drug >30 days after the last dose of study drug.

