6.2 Vital Signs

Blood pressure and heart rate will be measured at the time points specified in [Schedules 2, 3](#) and [4](#). Body temperature will be measured prior to randomization at Visit 1a. During the study, additional vital signs measurements will be performed if clinically indicated. Vital signs performed on dosing days should be obtained prior (within 60 minutes) to the start of the injection and between 10 to 30 minutes after completion of the injection of study drug. Every effort should be made to measure and record vital signs prior to any blood sample collection.

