	1		2		3		4		5		6		7		8		9		10		11		12	
	DOSING VISITS (1b to 24b)																							
	1b	2b	3b	4b	5b	6b	7b	8b	9b	10b	11b	12b	13b	14b	15b	16b	17b	18b	19b	20b	21b	22b	23b	24b
Physical exam ^b	X _d											X												X
Body Weight	X _d																							
Concomitant medications	X	X	X	X	X	X	X	X	X	X	X	X	X	X	X	X	X	X	X	X	X	X	X	X
Vital signs (BP, HR) ^c	X			X		X		X		X		X		X		X		X		X		X		X
Clinical safety lab testing (hematology, chemistry, coagulation)	X _d											X												X
Study drug administration	X ^e	X	X	X	X	X	X	X	X	X	X	X ^e	X	X	X	X	X	X	X	X	X	X	X	X ^e
Telephone contact ^f						X												X						
EQ-5D-Y/eDiary ^{g, h}	X _d								X								X							
Daily angioedema attack monitoring/eDiary ^h	X-----X																							
Adverse events	X-----X																							
PK/PD assessments	Details on timing of blood sample collection for PK/PD assessments is provided in Schedule 5.																							
Immunogenicity testing (C1 INH antibody)	X _d																							

eDiary=electronic study diary; EQ-5D-Y (Youth version of EQ-5D)=health-related quality of life descriptive system for youth

^a Study drug administration and scheduled procedures will occur twice weekly (every 3 or 4 days) during the 12-week treatment period (Treatment Period 2, Visits 1b-24b).

^b Physical examinations will be targeted based on reporting of adverse events and performed in accordance with standards at the site.

^c Vital signs will be measured using standard methods at each study site. On dosing days, vital signs should be obtained prior (within 60 minutes) to the injection of study drug and between 10 to 30 minutes after completion of the injection of study drug. Additional vital signs measurements may be performed if clinically indicated.

^d Specified study procedures and blood samples should be performed/collected prior to study drug administration, on the same day.

^e Study drug will be administered by qualified personnel to all subjects at the investigational site for Dosing Visits 1b, 12b, and 24b.

^f For those subjects who are dosed by a qualified home healthcare professional, study personnel will contact the parent/caregiver by telephone on Weeks 3 and 9 (after Dosing Visits 6b and 18b, respectively) to discuss and document study compliance, tolerability of CINRYZE dose, and adverse events. All telephone contacts will be documented in the source notes at the clinical site.

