11.3 Vital Signs

Descriptive statistics for vital signs (e.g. systolic and diastolic blood pressure and pulse) and their changes from baseline at each post-dose visit and final visit will be presented by treatment.

Vital sign values will be considered PCI if they meet the observed value criteria or the change from baseline criteria listed in [Table 7](#). A supportive listing of subjects with post-baseline PCI values will be provided. All vital signs results will be listed for the Safety Set.

Table 7 Criteria for Potentially Clinically Important Vital Signs

Vital Sign Parameter	Flag	Criteria
		Observed Value
Systolic blood pressure (mmHg)	High	Increase of ≥ 20 from baseline value and ≥ 140
	Low	Decrease of ≥ 20 from baseline value and ≤ 90
Diastolic blood pressure (mmHg)	High	Increase of ≥ 15 from baseline value and ≥ 90
	Low	Decrease of ≥ 15 from baseline value and ≤ 50
Pulse rate (beats per minute)	High	Increase of > 15 from baseline value and ≥ 100
	Low	Decrease of > 15 from baseline value and ≤ 45
Temperature ($^{\circ}\text{C}$)	High	> 38.3
	Low	< 35

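### After Visit 1a, no planned vital-sign summary or flag uses the same-visit pre-injection reading, so the acute post-injection change at 500 U and 1000 U is largely unsummarised

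*SAP*

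**What the plan says.** **Collection.** Schedule 2 of the protocol (footnote e) fixes the timing for visits at which study drug is given: "vital signs should be obtained prior (within 60 minutes) to the injection of study drug and between 10 to 30 minutes after completion". Schedule 3 (footnote c), Protocol 6.2 and the footnotes to the SAP's schedule tables repeat this timing. The vital signs are blood pressure and heart rate. For temperature, Protocol 6.2 says "Body temperature will be measured prior to randomization at Visit 1a", and the later schedules list only blood pressure and heart rate.

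**Baseline.** SAP Section 11 applies one rule to every safety variable: "the last value collected prior to the first dose of the investigational product will be used as baseline for all analyses". In practice this is the Visit 1a pre-dose reading.

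**Analysis.** SAP 11.3 plans descriptive statistics for vital signs, and "their changes from baseline at each post-dose visit and final visit will be presented by treatment". The blood pressure and pulse rows of SAP Table 7 combine a change from that baseline with an absolute limit; the low systolic row, for example, reads "Decrease of ≥ 20 from baseline value and ≤ 90". The planned outputs are Table 4.7.1 (actual values and change from baseline), Table 4.7.2 (subjects with PCI values) and Listing 8.2.

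**The concern.** Paired readings around an injection serve mainly to show the acute response to it. The SAP collects the pairs but takes differences from a single value. By the end of Period 2 that value is about 24 weeks old. Throughout Period 2 it also precedes 12 weeks on the other dose. Only Doses 1, 12 and 24 of each period must be given at the site, so many later readings may come from a different place. A change from Visit 1a therefore mixes any infusion effect with day-to-day, location and age-related variation.

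Safety and tolerability of the two doses is a secondary objective. At stake is whether the report can show, by dose, what blood pressure and pulse do in the half hour after an injection. There is also an ambiguity: with two readings per visit and no rule for choosing, Table 4.7.1 could be programmed on the pre-injection value, the post-injection value or a pool of both, and these answer different questions.

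**Working it through.** The plan gives no figure to reproduce here. The check counts the readings, traces which baseline each output uses, and illustrates the consequence.

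**1. Count of pairs.** The vital-signs row ("Vital signs (BP, HR) ^c") in the SAP's Period 2 schedule is marked at Visits 1b, 4b, 6b, 8b, 10b, 12b, 14b, 16b, 18b, 20b, 22b and 24b: 12 of 24 doses. The Period 1 row is not cleanly readable in the text available, so 12 is assumed there too.
- Pairs per child: 12 + 12 = 24.
- Pairs in 12 completing children: 24 × 12 = 288.
- Visits where the SAP baseline is the same-day pre-dose reading: 1 (Visit 1a), or 1/24 = 4%.
- Visits without a same-visit baseline: 23 per child, or 23 × 12 = 276 in all.

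**2. Outputs.** Tables 4.7.1 and 4.7.2 both work from the Section 11 baseline. Listing 8.2 shows raw values. No output contains post-injection minus same-visit pre-injection. The SAP defines a period-specific baseline for weight (SAP 11.1) but none for vital signs.

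**3. Effect on a flag.** Low systolic row of Table 7: fall of at least 20 mmHg and value at most 90 mmHg. The readings below are assumed.

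| SAP baseline | Same-visit pre | Post | Acute fall | Fall from SAP baseline | SAP flag | Same-visit flag |
|---|---|---|---|---|---|---|
| 105 | 110 | 88 | 22 | 17 | No | Yes |
| 112 | 95 | 90 | 5 | 22 | Yes | No |

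The SAP rule can miss an acute fall and can flag a day-to-day shift.

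**4. Noise in the change score.** With a common SD σ and correlation ρ between two readings, SD(change) = σ√(2(1−ρ)). Assume ρ = 0.4 to 0.6 with the distant baseline and 0.7 to 0.9 within a visit. The variance ratio (1−ρ_distant)/(1−ρ_visit) then runs from 0.4/0.3 = 1.3 to 0.6/0.1 = 6.0. These correlations are not in the documents.

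**5. Pulse, change part alone and full criterion.** Assume a between-day SD s_d and a within-visit SD s_w, with no infusion effect. SD of change from Visit 1a = √(2(s_d² + s_w²)); SD of the same-visit change = √2·s_w.

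| (s_d, s_w), bpm | SD from Visit 1a | SD same visit | P(change >15), Visit 1a | P(change >15), same visit |
|---|---|---|---|---|
| (6, 5) | 11.0 | 7.1 | 8.7% | 1.7% |
| (10, 5) | 15.8 | 7.1 | 17.1% | 1.7% |
| (12, 6) | 19.0 | 8.5 | 21.5% | 3.9% |

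The Table 7 high-pulse row also requires a pulse of at least 100. With both parts applied and an assumed mean pulse, the per-visit chance of a flag from the Visit 1a baseline, across the three SD pairs, is:
- mean 75 bpm: 0.1 to 2.7%
- mean 80 bpm: 0.4 to 5.3%
- mean 85 bpm: 1.8 to 8.9%
- mean 90 bpm: 4.4 to about 13%

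The same-visit pair gives 0.02 to 1.8% over the same range. The direction is stable; the size depends on the assumed SDs and mean.

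**6. Dose contrast.** Let B be the Visit 1a value. For a child with post-injection data on both doses, (post₁₀₀₀ − B) − (post₅₀₀ − B) = post₁₀₀₀ − post₅₀₀, so B cancels. What remains is (pre₁₀₀₀ − pre₅₀₀) + (acute₁₀₀₀ − acute₅₀₀). The contrast is therefore not distorted by an odd Visit 1a value, but it still carries the difference between the two pre-injection levels.

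**The case against.** A reader might infer that the acute effect of the injections is never analysed. The documents do not support that.
- At Visit 1a the SAP baseline is the same-day pre-dose reading. The Visit 1a post-injection change is therefore an acute effect, of 500 U in sequence A/B and 1000 U in B/A.
- Adverse events are summarised by onset during administration or within 24 hours (SAP 11; Table 4.3.1.2).
- All vital signs are listed, and 12 children can be read by eye.
- Vital signs are scheduled at about half of the doses, not at every injection.

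These points stand. They leave a gap because the Visit 1a contrast is between children and covers one dose each, adverse-event reporting relies on the judgement of staff who know the dose, and a listing is not a summary by dose.

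A reader might also infer that an atypical Visit 1a value biases the comparison of doses. It cancels within child, as step 6 shows, so that claim fails. If Table 4.7.1 showed both readings at each visit, the mean acute change could be recovered by subtraction for the same children, though not its spread. The SAP does not say that it will.

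It is tempting to quote 9 to 22% as chance flag rates. Those figures rest on assumed SDs and use only the change part of the pulse criterion; the full-criterion rates are lower.

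Finally, a pre-treatment baseline is a recognised choice for detecting sustained shifts, and Protocol 7.4 asks for changes from baseline. That argues for adding the same-visit change, not for replacing the existing one.

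The temperature row of Table 7 is not impossible to trigger. Protocol 6.2 allows additional vital signs when clinically indicated, and SAP 18.3 uses all post-baseline assessments for overall PCI determination.

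**Conclusion.** The point holds in a limited form. After Visit 1a, at about 23 of 24 vital-sign dosing visits per child, no planned summary or flag uses the same-visit pre-injection reading. SAP 11.3 also leaves open which reading represents a visit. The post-injection change at 500 U and 1000 U is thus summarised directly only for the first dose, and otherwise reached only indirectly. The count assumes that Period 1 has the same number of vital-sign visits as Period 2.

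The size of the effect on flags cannot be fixed from the documents, because they give no SDs, correlations or mean pulse. The direction is clear: the distant baseline adds noise, and it can both miss acute changes and flag unrelated ones. The primary analysis, the sample size and the significance level are unaffected. This is an inexpensive improvement to the reporting of a secondary objective, not a flaw that threatens the trial's conclusions.

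**What to change.** In SAP 11.3 and Table 4.7.1:

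1. Add the change from the same-visit pre-injection reading to the 10 to 30 minute post-injection reading, by treatment and visit, for blood pressure and pulse.
2. Present pre-injection and post-injection values separately, and state which is used in each summary. Keep the pre-first-dose baseline for the longer-term trend.
3. Report the Table 7 blood pressure and pulse change criteria for post-injection values against the same-visit pre-injection reading, in addition to the existing baseline. Flags for sustained drift are then kept.
4. Add a note that only unscheduled readings can trigger the temperature row after Visit 1a, or remove the row. No new measurement is needed.
5. While editing, align the sentence introducing Table 7, which treats the observed-value and change criteria as alternatives, with the blood pressure and pulse rows, which require both.

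The cost is SAP wording, one extended table shell and a further PCI column, all from data already collected. No protocol amendment or extra procedure is required.
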